#### **6.5 Duration of Follow Up**

The clinical course of each adverse event will be followed until resolution, stabilization, or until it has been determined that the study treatment or participation is not the cause.

Serious adverse events that are still ongoing at the end of the study period will necessitate follow-up to determine the final outcome. Any serious adverse event that occurs after the study period and is considered to be possibly related to the study treatment or study participation will be recorded and reported immediately.

Following completion of active treatment (EOT) and while still on study (Follow up), patients will be followed for survival as of standard of care for up to 1 year. This follow up can either be done as a visit to the study doctor's clinic or via telephone call to the patient.

## **7.0 Dose Delays/Dose Modifications**

Patients will receive a course of their treatment every 4 weeks, but not exceeding more than 8 weeks between treatment courses (4 weeks of treatment + a window of 4 weeks between cycles). Patients should receive their second course of therapy without interruption, regardless of their degree of myelosuppression. After the first two courses of therapy, the interval between subsequent cycles of Azacitidine therapy could be prolonged (with a maximum of 4 weeks prolongation between each 28 day cycle) at the discretion of the investigator. During any dose delays of Azacitidine, Ascorbic Acid therapy should not be delayed. Subsequent cycles can be given prior to baseline peripheral blood count recovery if considered to be in the best interest for the patient and after discussion with the principal investigator and the discussion documented in the patient's medical record.

No dose modification to azacitidine or ascorbic acid can occur during the treatment course.

## **8.0 Potential Risks and Adverse events**

### **8.1 Potential Risks**

#### **8.1.1 Azacitidine**

##### **COMMON, SOME MAY BE SERIOUS**

In 100 people receiving azacitidine more than 20 and up to 100 may have:

**COMMON, SOME MAY BE SERIOUS**

In 100 people receiving azacitidine more than 20 and up to 100 may have:

- Fever
- Fatigue
- Headache
- Nausea
- Vomiting
- Diarrhea
- Constipation
- Loss of appetite
- Bruising
- Low blood cell counts
- Weakness
- Joint pain
- Shivering
- Cough
- Difficulty Breathing

**OCCASIONAL, SOME MAY BE SERIOUS**

In 100 people receiving azacitidine from 4 to 20 may have:

- Chest pain
- Pale skin
- Swelling (such as in arms and legs)
- Abnormal heart sound
- Fast heart beat
- Low blood pressure
- High blood pressure
- Fainting
- Dizziness
- Anxiety
- Depression
- Difficulty sleeping
- Lack of energy
- Numbness
- Pain
- Skin hives and /or rash
- Dry skin and /or itching
- Sweating
- Low blood levels of potassium
- Weight loss
- Abdominal pain, tenderness, and/or swelling
- Mouth blisters
- Upset stomach
- Hemorrhoid bleeding
- Difficulty swallowing
- Sore or painful throat

**OCCASIONAL, SOME MAY BE SERIOUS**

In 100 people receiving azacitidine from 4 to 20 may have:

- Difficult and/or painful urination
- Blood in urine
- Pain
- Stuffy and/or runny nose
- Wheezing
- Lymph node swelling
- Infection
- Hair loss

**RARE, AND SERIOUS**

In 100 people receiving azacitidine 3 or fewer may have:

- Irregular heartbeat
- Heart failure
- Stoppage of heart and lung function
- Bleeding in and/or around the brain
- Seizure
- Skin condition with fever and skin lesions
- Abnormal Blood acid/base balance (possible organ damage)
- Dehydration
- Inflammation of the gallbladder
- Terry or coffee ground-like blood in the stool
- Enlarged spleen
- Liver failure
- Kidney failure, even requiring dialysis
- Build-up of bodily waste products in the blood
- Coughing up blood
- Lung inflammation (possible difficulty breathing)
- Allergic reaction, which may be life-threatening
- Body-wide inflammation
- Breakdown products of the cancer cells entering the blood stream

Azacitidine may cause you to develop another type of cancer such as leukemia, a type of blood cancer

### 8.1.2 Ascorbic Acid

### **COMMON, SOME MAY BE SERIOUS**

In 100 people receiving ascorbic acid more than 20 and up to 100 may have:

- Fatigue
- Headache
- Nausea
- Vomiting
- Diarrhea
- Constipation
- Loss of appetite
- Bruising
- Low blood cell counts
- Weakness
- Joint pain
- Shivering
- Cough
- Difficulty Breathing

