### **1.3 Name and Description of Ascorbic Acid**

Ascorbic acid is a water-soluble vitamin. Ascorbic acid has few strictly pharmacological actions. Administration in amounts greatly in excess of physiologic requirements causes no demonstrable effects. The vitamin is an essential coenzyme for collagen formation, tissue repair and synthesis of lipids and proteins. It acts both as a reducing agent and as an antioxidant and is necessary for many physiologic functions, e.g., metabolism of iron and folic acid, resistance to infection, and preservation of blood vessel integrity. Signs and symptoms of early AA deficiency include malaise, irritability, and arthralgia, hyperkeratosis of hair follicles, nosebleed, and petechial hemorrhages. Prolonged deficiency leads to clinical scurvy.

Ascorbic acid is normally present in both plasma and cells. The absorbed vitamin is ubiquitous in all body tissues. The highest concentrations are found in glandular tissue, the lowest in muscle and stored fat. Ascorbic acid is partially destroyed and partially excreted by the body. There is a renal threshold for AA; the vitamin is excreted by the kidney in large amounts

only when the plasma concentration exceeds this threshold, which is approximately 1.4 mg/100 mL. When the body is saturated with ascorbic acid, the plasma concentration will be about the same as that of the renal threshold; if further amounts are then administered, most of it escapes into the urine. When body tissues are not saturated and plasma concentration is low, administration of ascorbic acid results in little or no renal excretion.

A major route of metabolism of ascorbic acid involves its conversion to urinary oxalate, presumably through intermediate formation of its oxidized product, dehydro-ascorbic acid. In a study of healthy volunteers at the NIH, an in-hospital depletion-repletion study was conducted. Seven healthy volunteers were hospitalized for 4-6 months and consumed a diet containing <5 mg of AA daily. Steady-state plasma and tissue concentrations were determined at seven daily doses of vitamin C from 30 to 2500 mg. AA steady-state plasma concentrations as a function of dose displayed sigmoid kinetics. Complete plasma saturation with AA occurred at 1000 mg PO daily.

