Ascorbic Acid has also been investigated in clinical trials. One study reported three case reports of cancer patients who received IV ascorbic acid as their main therapy . During ascorbic acid therapy, the patients used additional treatments, including vitamins, minerals, and botanicals. According to the authors, the cases were reviewed in accordance with the NCI Best Case Series guidelines. Histopathologic examination suggested poor prognoses for these patients, but they had long survival times after being treated with IV ascorbic acid . Ascorbic Acid was given at doses ranging from 15 g to 65 g, initially once or twice a week for several months; two patients then received it less frequently for 1 to 4 years. Two studies demonstrated that IV ascorbic acid treatment resulted in improved quality of life and decreases in cancer-related side effects in cancer patients . Studies have shown that ascorbic acid can be safely administered to healthy volunteers or cancer patients at doses up to 1.5 g/kg and with screening to eliminate treating individuals with risk factors for toxicity (e.g., glucose-6-phosphate dehydrogenase deficiency, renal diseases, or urolithiasis). These studies have also found that plasma concentrations of ascorbic acid are higher with IV administration than with oral administration and are maintained for more than 4 hours .

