## **4.2 Exclusion Criteria**

The presence of any of the following will exclude a subject from study enrollment:

- 4.2.1 Any prior treatment with azacitidine or decitabine.
- 4.2.2 Patients diagnosed with APL, AML-M3.
- 4.2.3 Patients receiving other active treatment for their myeloid malignancy including investigational agents with the exception of hydrea for WBC control.
- 4.2.4 Nursing or pregnant women.
- 4.2.5 History of allergic reactions to either azacitidine or ascorbic acid.
- 4.2.6 Patients with uncontrolled intercurrent illness including, but not limited to ongoing or active infection, symptomatic congestive heart failure, unstable angina pectoris, cardiac arrhythmia, or psychiatric illness/social situations that would limit compliance with study requirements.

4.2.7 Patients with higher risk of bleeding (deemed by the treating physician) or on anticoagulation.

4.2.8 Patients who are unwilling or unable to comply with all study requirements.

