### **OCCASIONAL, SOME MAY BE SERIOUS**

In 100 people receiving ascorbic acid from 4 to 20 may have:

- Pale skin
- Swelling (such as in arms and legs)
- Abnormal heart sound
- Fast heart beat
- Low blood pressure
- High blood pressure
- Fainting
- Dizziness
- Anxiety
- Depression
- Lack of energy
- Numbness
- Pain
- Skin hives and /or rash
- Dry skin and /or itching
- Sweating

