### **RARE, AND SERIOUS**

In 100 people receiving ascorbic acid 3 or fewer may have:

- Kidney stones
- Kidney failure
- Bleeding that could be life threatening
- Loss of blood due to hemolysis (a process where red cell gets destructed)

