### **8.2.3 Adverse Event Evaluation**

The investigator or designee is responsible for ensuring that all adverse events (both serious and non-serious) observed by the clinical team or reported by the subject, which occur after the

subject has signed the informed consent are fully recorded in the subject's medical records. Source documentation must be available to support all adverse events.

The investigator or sub-investigator (treating physician if applicable) or delegated staff will provide the following for all adverse events (both serious and non-serious):

- Event term (as per CTCAE 4.1)
- Description of the event
- Date of onset and resolution
- **Expectedness of the toxicity**
- **Grade of toxicity**
- **Attribution of relatedness to the investigational agent- (this must be assigned by an investigator, sub-investigator, or treating physician)**
- Action taken as a result of the event, including but not limited to; no changes, dose interrupted, reduced, discontinued, etc. or action taken with regard to the event, i.e. no action, received conmed or other intervention, etc.
- Outcome of event

**An expected adverse event** is an event previously known or anticipated to result from participation in the research study or any underlying disease, disorder, or condition of the subject. The event is usually listed in the Investigator Brochure, consent form or research protocol.

**An unexpected adverse event** is an adverse event not previously known or anticipated to result from the research study or any underlying disease, disorder, or condition of the subject.

**Attribution** is the relationship between an adverse event or serious adverse event and the study drug. Attribution of any adverse event can only be assessed by the PI and/or Co-I. Attribution will be assigned as follows:

- Definite – The AE is clearly related to the study drug.
- Probable – The AE is likely related to the study drug.
- Possible – The AE may be related to the study drug.
- Unlikely – The AE is doubtfully related to the study drug.
- Unrelated – The AE is clearly NOT related to the study drug.

Protocol must specify if attribution is required for individual components of the treatment regimen or the treatment regimen as a whole.

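### Every common and occasional ascorbic acid risk in Section 8.1.2 is also an azacitidine item, conflicts with Section 1.3, and is an unsound reference for expectedness per agent

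*Combined protocol and SAP*

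**What the plan says.** Section 8.1 gives risks by agent in three frequency bands. For azacitidine (8.1.1) the top band opens with "In 100 people receiving azacitidine more than 20 and up to 100 may have". For ascorbic acid (8.1.2) the same band opens with "In 100 people receiving ascorbic acid more than 20 and up to 100 may have", and the middle band with "In 100 people receiving ascorbic acid from 4 to 20 may have". The ascorbic acid rare list has four entries of its own: kidney stones, kidney failure, life-threatening bleeding, and "Loss of blood due to hemolysis (a process where red cell gets destructed". Section 9.0 sends the reader to Section 8.1 for the adverse events of both agents.

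Section 1.3 says of ascorbic acid: "Administration in amounts greatly in excess of physiologic requirements causes no demonstrable effects". It also reports minimal adverse effects from 50 to 100 g per infusion in a phase I pancreatic cancer study. It says that doses up to 1.5 g/kg were given safely in earlier studies "with screening to eliminate treating individuals with risk factors for toxicity (e.g., glucose-6-phosphate dehydrogenase deficiency, renal diseases, or urolithiasis".

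Section 8.2.3 defines an expected event as one anticipated from taking part in the study or from the underlying disease, and adds: "The event is usually listed in the Investigator Brochure, consent form or research protocol". The section ends with a template instruction that the protocol must state whether attribution applies to each component or to the regimen as a whole. No such statement follows.

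On eligibility, the only exclusion that names ascorbic acid is "History of allergic reactions to either azacitidine or ascorbic acid". Inclusion criterion 4.2.8 leaves normal organ and marrow function to the discretion of the treating physician and the principal investigator.

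**The concern.** Ascorbic acid is the one agent added to standard azacitidine, and the safety of the combination is the first secondary objective. The protocol's reference list for that agent should therefore describe that agent. As written, it says that more than 20 in 100 people receiving ascorbic acid may have low blood cell counts. That is a familiar azacitidine effect, and nothing in Section 1.3 supports it for ascorbic acid.

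What is at stake is how safety events are classified. With attribution by component left open, two investigators could handle the same event differently. One could judge a reaction attributed to ascorbic acid against 8.1.2 and call it expected, on a frequency with no source in the documents.

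A second, separate inconsistency concerns the rare list. It names kidney stones, kidney failure and hemolysis as ascorbic acid risks, and Section 1.3 names the patient factors that earlier studies screened out. The eligibility section takes up neither explicitly.

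**Working it through.** No sample size or error-rate formula applies. The check is a comparison of the lists, followed by a reading of the linked sections.

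**Step 1. Are the ascorbic acid items contained in the azacitidine lists?** Inputs are the common and occasional lists in 8.1.1 and 8.1.2, compared for exact wording, order and band.

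| Band | Azacitidine, distinct items | Ascorbic acid items | Matched, same order | Azacitidine items not repeated |
|---|---|---|---|---|
| Common (more than 20 per 100) | 15 | 14 | 14 of 14 | 1 (Fever) |
| Occasional (4 to 20 per 100) | 33 (34 lines, Pain twice) | 16 | 16 of 16 | 17 |
| Total | 15 + 33 = 48 | 14 + 16 = 30 | 30 of 30 | 48 − 30 = 18 |

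The 16 occasional items are the first 18 lines of the azacitidine occasional list with chest pain and difficulty sleeping removed (18 − 2 = 16). The later azacitidine lines, such as low potassium, weight loss, infection and hair loss, are absent. The ascorbic acid lists are thus an ordered subset of the azacitidine lists. The rare list is not copied.

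**Step 2. Do the frequencies fit the rest of the protocol?** Section 8.1.2 puts low blood cell counts, bruising, shivering and difficulty breathing above 20 per 100. Section 1.3 reports no demonstrable effects from large excess amounts and minimal adverse effects at 50 to 100 g per infusion. It does mention severe side effects in some patients, but in regimens that also contained arsenic trioxide. No passage supplies a source for the frequencies in 8.1.2.

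**Step 3. Does the list change what counts as expected?**
- *Expectedness judged for the regimen:* all 30 events are already listed for azacitidine, so 8.1.2 adds 30 − 30 = 0 expected events from these two bands.
- *Expectedness judged per agent:* all 30 become expected for ascorbic acid. The clearest case is days −3 to −1, when ascorbic acid is given before any azacitidine. Azacitidine delays of up to 4 weeks (Section 7.0), when ascorbic acid continues, are a weaker case because the patient has recently had azacitidine.

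Section 8.2.3 does not say which of the two applies.

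**Step 4. Are the risk factors in Section 1.3 carried into eligibility or screening?**

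| Factor in 1.3 | Related risk in 8.1.2 | Named exclusion | Other coverage |
|---|---|---|---|
| G6PD deficiency | Hemolysis | No | No test in 11.1.1 or Appendix VI |
| Renal diseases | Kidney failure | No | Inclusion 4.2.8, discretionary; BUN and creatinine in the panel |
| Urolithiasis | Kidney stones | No | General history only; no stone history named |

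Named exclusions: 0 of 3. One of the three, renal disease, can be reached through the discretionary criterion.

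**Step 5. Dose context.** Section 1.3 refers to doses up to 1.5 g/kg; this trial gives 1 g/day by mouth. The documents give no body weight. Assuming 70 kg, 1.5 × 70 = 105 g, about 105 times the trial dose. Assuming 50 to 100 kg, the range is 75 to 150 times.

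**The case against.** The strongest reply is that little follows in practice. Section 8.2.3 defines expectedness for the study and the disease, not per agent, and says only that expected events are usually listed. All 30 events are expected under azacitidine, and several could be expected from the disease itself. Every serious event goes to the lead investigator within 24 hours (8.4.1) and to the Data and Safety Toxicity Committee (8.6), whatever its expectedness. The safety endpoint in Section 14.0 counts adverse events and drug-related grade 3 or 4 toxicity, and expectedness does not enter it. All of this stands. It limits the consequence, but it does not make the list correct or settle which reading of 8.2.3 applies.

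A reader might infer that serious ascorbic acid events are being hidden. The reporting rules do not support that. Onward reporting to the FDA and IRB is made as applicable, so an effect there is possible but not shown.

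A reader might also infer that patient selection is wrong. The documents do not show this either. Section 1.3 describes what other studies did, at far higher doses and in a paragraph mainly about intravenous use. Nothing says the same screening is needed at 1 g/day by mouth. Renal disease can be caught under inclusion 4.2.8, chemistry and hematology are repeated on day 1 of each cycle, patients at higher bleeding risk are excluded, and toxicity criteria end treatment (Section 6.4). What remains is that 8.1.2 lists hemolysis, kidney stones and kidney failure for this trial's agent, while G6PD deficiency and urolithiasis appear nowhere in eligibility or screening and no reason is given.

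**Conclusion.** The common and occasional ascorbic acid lists in 8.1.2 are in error: 30 of 30 entries coincide with azacitidine entries in wording, order and band, and they conflict with Section 1.3. That they were copied is an inference from the match, but a strong one. It would be too much to say that the two agents' lists are identical, since 18 of the 48 azacitidine items are not repeated and the rare list is specific to ascorbic acid.

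The effect on expectedness is conditional. It arises only if expectedness is judged per agent, and then most clearly in the three-day lead-in; at regimen level it is nil. The unfilled attribution line in 8.2.3 is what leaves this open.

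The eligibility part is a request to reconcile Sections 1.3, 4 and 8.1.2, or to explain the difference for this regimen. It is not a finding that the criteria are wrong. The primary endpoint, sample size, type I error and power are untouched. The correction is worth making because it is cheap and because Section 8.1 is the protocol's adverse event list for the added agent.

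**What to change.** 1. Replace the common and occasional lists in 8.1.2 with events and frequencies specific to ascorbic acid, drawn from a source the sponsor can cite. The documents reviewed do not supply such frequencies.
2. Check the consent form for the same error. It is not among the documents reviewed, so a match cannot be assumed.
3. Replace the template line in 8.2.3 with a rule that attribution and expectedness are judged for each component, against the corrected list for that component.
4. Reconcile Section 1.3 (factors screened out in earlier studies), Section 4 (inclusion 4.2.8 and the exclusion list) and the rare list in 8.1.2, or state why they differ for 1 g/day by mouth. Which eligibility rule is right is a clinical decision for the sponsor.

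The cost is a wording amendment, with a consent revision if the check finds the error there. Some events may move from expected to unexpected for ascorbic acid. No new procedure is needed unless the sponsor decides to change screening.

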### **OCCASIONAL, SOME MAY BE SERIOUS**

In 100 people receiving ascorbic acid from 4 to 20 may have:

- Pale skin
- Swelling (such as in arms and legs)
- Abnormal heart sound
- Fast heart beat
- Low blood pressure
- High blood pressure
- Fainting
- Dizziness
- Anxiety
- Depression
- Lack of energy
- Numbness
- Pain
- Skin hives and /or rash
- Dry skin and /or itching
- Sweating

### **RARE, AND SERIOUS**

In 100 people receiving ascorbic acid 3 or fewer may have:

- Kidney stones
- Kidney failure
- Bleeding that could be life threatening
- Loss of blood due to hemolysis (a process where red cell gets destructed)

## 8.2 Definitions

### 8.2.1 Adverse Event

An **adverse event** (AE) is any unfavorable or unintended event, physical or psychological, associated with a research study, which causes harm or injury to a research participant as a result of the participant's involvement in a research study. The event can include abnormal laboratory findings, symptoms, or disease associated with the research study. The event does not necessarily have to have a causal relationship with the research, any risk associated with the research, the research intervention, or the research assessments.

Adverse events may be the result of the interventions and interactions used in the research; the collection of identifiable private information in the research; an underlying disease, disorder, or condition of the subject; and/or other circumstances unrelated to the research or any underlying disease, disorder, or condition of the subject.

Abnormal laboratory results will be assessed in real time by the physicians. Treatment for any clinically significant values will be completed in real documented in the physician's note. Documentation for the assessment and treatment will be provided in the physician's note as source documentation.

Clinical staff (i.e. nurses, clinical research coordinators) can be delegated to evaluate and assess all adverse events, with the exception of determining relationship to study treatment. These assessments will require documented review by either the treating physician or PI.

